9.3.2 Quality of Life Assessments

For each of the QoL measures examined in this study, we will provide simple descriptive and comparative analyses by ITT. To address the potential for multiple comparisons problems arising from testing each individual scale and time point separately, we propose two complementary approaches. First, we will pre-specify the SAQ summary score as the primary QoL comparison of interest and assign all other comparisons to a secondary (supportive) status. Second, we will use a mixed model repeated measures with the baseline score as a covariate, Day 45, Month 6, and Month 12 responses included as outcome variables, and time as a fixed variable. Restricted maximum likelihood estimation will be used to model all available data from each participant without imputing missing values. Change in QoL from baseline to follow-up will be assessed by the mixed models method using an intention to treat approach. Further details of these analyses are contained in a separate PRECISE Economics and QoL SAP.

9.3.3 Additional Analyses

9.3.3.1 Time to Death

Deaths will be classified by the CEC as to whether the mode of death was due to a cardiovascular (CV) or non-cardiovascular (non-CV) cause. If insufficient source document is obtained to allow CEC adjudication of the cause of death, and the CEC classifies the cause of death as “unknown,” then the site-reported cause of death will be used if available. If neither the site nor the CEC can provide a classification of the cause of death, the death will not be considered as a cardiovascular death.

The following death endpoints will be analyzed:

- All-cause death
- CV death (including sudden death)
- Non-CV death

For all-cause death endpoint the log-rank test will be the primary statistical methodology to test for outcome differences between precision care arm and usual care arm. The Cox proportional hazards model will be used to estimate the average treatment effect size using the hazard ratio

(HR) and 95% confidence interval (CI) with treatment assignment as the only covariate in the model. Cumulative event rates will be calculated according to the method of Kaplan-Meier for each randomized arm as a function of time from randomization to the time of event or censoring + 1, and the estimated event probabilities will be displayed graphically. For CV death endpoint the competing risks methodology of Fine-Gray (Fine and Gray 1999) will be utilized, where death due to a non-CV cause is considered as a competing risk in analyzing endpoints with CV death as a component. This methodology, rather than treating non-CV death as a censoring event, estimates the cumulative cause-specific function, and is performed within the proportional hazards framework using the marginal failure sub-distribution associated with the event of interest (CV death). Cumulative incidence rates, sub-distribution hazard ratios with 95% CIs, and Wald p-values will be calculated with the Fine-Gray framework. As supplemental analyses, however, this endpoint will also be examined using (a) only the deaths classified by the CEC as CV; and, (b) deaths classified by the CEC as CV, but also including any deaths in the CV category that are classified as unknown by the CEC. Similar analyses will be conducted for non-CV death endpoint in which death is not a part of the endpoint of interest within the Fine-Gray competing risks framework.

9.3.3.3 Preventive Medication Use

New and total use of preventative medication will be collected during baseline and the participant follow-up at 45 days, 6 months and 12 months, the medication classes of interest will be defined as the following:

- Antiplatelet usage is defined as the usage of any of the following medications: ASA, Clopidogrel, Ticagrelor, or Prasugrel
- Lipid Lowering Medication usage is defined as the usage of any of the following medications: Statins or Other Lipid Lowering Agents
- Anti-Hypertensive Medication usage is defined as the usage of any of the following medications: Calcium Channel Blockers, Beta-Blockers, ACE-Inhibitor/ARB/ARNI, or Diuretic

The number (%) will be summarized between the precision care arm and usual care arm and compared using Pearson's chi-square test for the following combinations: 1) usage at baseline and 45 days, 2) usage at baseline and 6 months, and 3) usage at baseline and 12 months.

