Participants randomized to the precision evaluation arm will be assigned a management approach based on their PROMISE Risk Score, a risk model based on pre-test clinical characteristics derived from the PROMISE trial and validated in SCOT-HEART³⁴ or the presence of known non- obstructive atherosclerosis. Participants will be assigned to either 1) guideline-recommended medical management without planned testing (low risk) or 2) cCTA with selective FFR_{CT} (elevated risk or those with known plaque, independent of the PROMISE Risk Tool assessment). Participants assigned to the strategy of guideline-recommended medical management without planned testing will be treated with risk-appropriate preventive care and symptom control (including therapeutic trials of anti-anginal medications). Participants and their providers will be provided informational materials demonstrating the safety of this strategy based on pre-test probabilities and the PROMISE Risk Score. Participants with intractable symptoms despite maximal medical management whose clinicians opt for further testing (crossovers) will undergo cCTA with selective FFR_{CT}.

Participants undergoing cCTA as the initial test (both assigned or crossover) should have FFR_{CT} analysis ordered if cCTA shows at least one 30-90% stenosis in epicardial vessels of 2mm diameter or greater. Image sets will be sent promptly to HeartFlow for analysis and results will be returned to sites in < 24 hours to enable rapid incorporation into clinical decision making.

V.D. Participant Follow-Up

Participants will be followed up at 45 (+/-14) days and at 6 and 12 months (+/- 30 days) after enrollment. For US participants, follow-up at 45 days and at 6 and 12 months will be done by phone interviews conducted by the DCRI Outcomes Call Center, unless not allowed by their enrolling site. For participants outside of the US, follow-up will be conducted by the site coordinators.

Activities to be conducted at each follow up contact are described below and in the Schedule of Events.

45 (+/-14) day follow-up visit (in-person, portions may be done by phone) At the 45-day follow-up visit, participants will be asked the following:

- Assessment if any MACE has occurred since enrollment

- CV Update: Review and documentation of any cardiovascular diagnostic test, cardiovascular procedure, or hospitalizations/clinic visits due to cardiovascular symptoms and complications since enrollment

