unlikely (by definition) to have significant obstructive CAD. The managing clinician is encouraged to treat them with guideline-recommended preventive care, anti-anginal medications and other medical therapy as deemed appropriate to their clinical circumstances. This is expected to control or eliminate symptoms in most participants. In the unlikely event that symptoms are intractable or accelerating, despite reasonable medical treatment or if other compelling reasons for additional evaluation are present, testing may be warranted.

Unless there are urgent or emergent indications to proceed with invasive testing, all such participants requiring testing should have a cCTA followed by selective FFR_{CT} rather than stress testing or elective invasive catheterization. cCTA with selective FFR_{CT} should only be pursued if the participant is having:

1. Unstable/accelerating symptoms (i.e. no longer falls into stable angina cohort)
2. Continued stable symptoms despite risk factor modification including:
 - a) Optimized blood pressure control with goal <130/80 mmHg
 - b) Optimized lipid management with high-intensity statin in appropriate patients
 - c) Optimized diabetes management with blood glucose control in appropriate patients
 - d) Antiplatelet therapy in appropriate patients
 - e) Tobacco cessation in patients who smoke
 - f) Lifestyle counseling regarding diet exercise and stress reduction
 - g) Anti-anginal therapy including utilization of beta-blockers, calcium channel blockers, short and long-acting nitrates, and/or ranolazine

The assignment to no immediate testing is not time limited and is valid for the duration of the participant's enrollment in the trial. Testing in such participants should be infrequent and the reasons for this will be carefully documented and monitored.

V.F. Participant Withdrawal

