Participants undergoing cCTA as the initial test (both assigned or escalation) should have FFR_{CT} analysis ordered only if cCTA shows at least one 30-90% stenosis in epicardial vessels of 2 mm diameter or greater. Image sets will be sent promptly to HeartFlow for analysis and results will be returned to sites in less than 24 hours to enable rapid incorporation into clinical decision making.

Regardless of randomization or evaluation assignment, all participants will be treated with risk-appropriate preventive care and symptom control (including therapeutic trials of anti-anginal medications) as indicated.

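### The anti-hypertensive row in SAP 9.3.3.3 counts beta-blockers and calcium channel blockers whatever the reason for use, so it may mix symptom treatment with prevention (minor)

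*SAP*

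**What the plan says.** SAP 9.3.3.3 sets up three medication classes under the heading of preventive use: antiplatelet, lipid-lowering and anti-hypertensive. The third reads: "Anti-Hypertensive Medication usage is defined as the usage of any of the following medications: Calcium Channel Blockers, Beta-Blockers, ACE-Inhibitor/ARB/ARNI, or Diuretic". Each class is to be summarised by arm and "compared using Pearson's chi-square test for the following combinations", which pair baseline with 45 days, 6 months and 12 months. SAP 9.1 plans no multiplicity adjustment for tests of this kind.

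SAP 4.1.2 item 4 defines the preventive-medication endpoint more narrowly, as aspirin or other antiplatelet drugs and/or statins in participants with an indication. Protocol IV.C item 7 and VII.B agree. The anti-hypertensive class is thus an addition in 9.3.3.3, and that section does not repeat the indication restriction.

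On treatment, Protocol V.C says: "Participants assigned to the strategy of guideline-recommended medical management without planned testing will be treated with risk-appropriate preventive care and symptom control". Protocol V.E says that managing clinicians are "encouraged to treat them with guideline-recommended preventive care, anti-anginal medications and other medical therapy as deemed appropriate". For deferred participants whose stable symptoms continue, V.E reserves cCTA for symptoms that persist despite a list of measures, one of which is "Anti-anginal therapy including utilization of beta-blockers, calcium channel blockers, short and long-acting nitrates, and/or ranolazine". SAP section 2 says that usual care starts with a test in every participant.

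**The concern.** The same two drug classes have two roles. In the SAP row they count as blood-pressure prevention. In Protocol V.E they are symptom treatment, tied to a step that only deferred precision participants face. A normotensive deferred participant given a calcium channel blocker for chest pain would be coded as a new preventive anti-hypertensive user.

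If such starts are more frequent in the precision arm on balance, the row will show an excess that is partly the deferral strategy's own symptom treatment, and a reader could take it for better prevention. Preventive treatment is part of the protocol's rationale for cCTA (III.A), so the row would attract attention. The class also feeds the association between medication use and motivation in SAP 9.3.3.6 item 5. That analysis does not compare arms, so there the issue is only what the variable means.

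**Working it through.** The documents give no rate, effect size or power for medication use, so there is no plan figure to reproduce. The check sets the texts side by side and then illustrates the possible size.

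**Text comparison**

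- Classes in the SAP row: calcium channel blockers, beta-blockers, ACE-inhibitor/ARB/ARNI, diuretics.
- Classes named as anti-anginals in Protocol V.E: beta-blockers, calcium channel blockers, nitrates, ranolazine.
- Overlap: beta-blockers and calcium channel blockers. Nothing in 9.3.3.3 separates the two uses.

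**Inputs from the documents**

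- 1050 per arm; about 20% of the precision arm deferred, or 0.20 × 1050 = 210 participants; 10% attrition, leaving 945 per arm (SAP section 7).
- Two-sided 5% test, as in the sample-size section.

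**Assumed inputs**

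- x: the net excess, in the deferred group, of participants counted only because of a beta-blocker or calcium channel blocker. Range 5 to 30 points.
- Background use p0 of the whole class: 40%, 60% or 70%.
- The endpoint is treated as a simple proportion using the class at one follow-up time.

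**Formulas**

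Arm-level difference: d = deferred share × x.

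Chance of a significant result favouring precision care: P = Φ[(d − 1.96·SE0)/SE1]. Here p1 = p0 + d and p̄ = (p0 + p1)/2; SE0 = √[2p̄(1 − p̄)/n] and SE1 = √{[p0(1 − p0) + p1(1 − p1)]/n}. With no difference, P would be 2.5% in this direction.

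Worked case: x = 20 points, share 20%, p0 = 60%, n = 1050. Then d = 0.20 × 0.20 = 0.04, p1 = 0.64, p̄ = 0.62, SE0 = 0.021184 and SE1 = 0.021166. The argument of Φ is (0.04 − 0.04152)/0.021166 = −0.072, so P = 47.1%.

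| x (points) | d at 20% share | P, p0 = 40% | P, p0 = 60% | P, p0 = 70% | d at 10% share | P, p0 = 60% |
|---|---|---|---|---|---|---|
| 5 | 1.0 | 6.8% | 6.8% | 7.2% | 0.5 | 4.2% |
| 10 | 2.0 | 15.2% | 15.4% | 17.1% | 1.0 | 6.8% |
| 20 | 4.0 | 45.9% | 47.1% | 53.2% | 2.0 | 15.4% |
| 30 | 6.0 | 79.3% | 81.3% | 87.3% | 3.0 | 29.2% |

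With 945 per arm, a 20% share and p0 = 60%, the four values are 6.5%, 14.3%, 43.3% and 77.1%.

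The 10% share is shown because SAP 6.1 bases the low-risk cut point on the top 10% of the PROMISE cohort, and SAP section 6 moves known atherosclerosis to elevated risk.

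A just-significant whole-arm difference is 3.8 to 4.2 points over these background rates. At a 20% share that needs x of about 19 to 21 points (for example 4.15/0.20 = 20.8 at p0 = 60%); at a 10% share and p0 = 60% it needs 4.15/0.10 = 41.5.

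**The case against.** The strongest reply is that the treatment difference between arms is weaker than it looks. SAP section 6 says that, regardless of assignment, "all participants will be treated with risk-appropriate preventive care and symptom control (including therapeutic trials of anti-anginal medications) as indicated". The protocol synopsis also recommends anti-anginal treatment for all participants, and Protocol IV.F says that no specific medical treatment is mandated. A reader might infer from V.E that only the precision arm receives these drugs, and hence that it will show a false gain. The documents do not support that. Usual-care participants may start anti-anginals too, including after their test, so the net difference could be small or reversed. What stands is that the step before cCTA applies only to deferred precision participants.

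Second, not all of an excess would be artefact. The same V.E list includes "Optimized blood pressure control with goal <130/80 mmHg", so some added use would be real blood-pressure treatment. This is a reason for separate rows, because the combined row cannot show which part is which.

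Third, the planned tables (SAP section 10) split precision care into its no-testing and CTA groups and usual care by risk. That would show where an excess arises, but not why the drug was given.

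Fourth, a reader might look to the low-risk stratum, where nothing dilutes the effect: with 210 per arm and 60% background use, x = 10 points gives a 57.5% chance of significance and x = 20 gives 99.5%. However, 9.3.3.3 specifies no test in that stratum. SAP 9.3.3.4 states a repeat by risk group explicitly for radiation; 9.3.3.3 does not.

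**Conclusion.** The point holds as a minor one. The row, as defined, cannot separate anti-anginal from anti-hypertensive use, and one arm contains a step that names two of its four drug groups as symptom treatment. The comparison may therefore mix the two purposes, by an amount and in a direction that the documents do not determine.

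The 1 to 6 point range and the 7% to 81% chance rest on assumed start rates, a 20% deferred share, 60% background use and 1050 per arm. At a 10% share the same start rates give 0.5 to 3 points and 4% to 29%.

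A reader might also infer that the trial's preventive-medication endpoint is compromised. It is not: the listed endpoint covers only aspirin/antiplatelet drugs and/or statins, which these classes cannot enter. The primary endpoint and the Benjamini-Hochberg secondary endpoints are likewise untouched.

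**What to change.** In SAP 9.3.3.3, report beta-blockers and calcium channel blockers as a separate dual-use (anti-anginal/anti-hypertensive) row, apart from ACE-inhibitor/ARB/ARNI and diuretics. Show the combined anti-hypertensive class among participants with hypertension recorded at baseline, in line with the indication restriction in 4.1.2. Use the same derived variables in 9.3.3.6 item 5.

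The cost is one or two extra table rows. The SAP already names the drug classes, and baseline hypertension is an input to the PROMISE score, so no new data are needed. The hypertension restriction alone does not remove anti-anginal use among hypertensive participants, which is why the separate row is the more important part. In that row, some use that is truly for blood pressure will sit outside the ACE-inhibitor/ARB/ARNI and diuretic line.

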Endpoints will be assessed at 45 days, 6 months, and 1 year. Secondary endpoints include:

1. Hierarchical analysis (Finkelstein and Schoenfeld (FS) and Pocock's win ratio) of primary endpoint (gives priority to clinical importance of the components of the composite outcome rather than time to event)
2. Resource use patterns (all participants) and medical costs (US participants): resources to be assessed include index testing, follow up testing, diagnostic and other cardiac procedures and hospitalizations. Primary comparisons will be made at 12 months.
3. QoL: the Seattle Angina Questionnaire (SAQ) will be used to assess angina-specific Quality of Life; the EuroQol 5D (EQ-5D-5L) survey will be used for a brief assessment of overall (generic) health status; patient satisfaction with diagnostic process will be assessed once at 45 days using a 4-item instrument created for this trial.
4. Death: All-cause, cardiovascular, non-cardiovascular
5. Myocardial infarction: All, procedural, spontaneous MI
6. Hospitalizations: All, cardiovascular, non-cardiovascular, and for progressive or unstable angina
7. Rates of preventive medication use (ASA, statins) in participants with clinical indication for use: hyperlipidemia, diabetes, documented CAD
8. Cumulative radiation exposure at 1 year
9. Proportion of invasive coronary angiogram patients who undergo revascularization (PCI or CABG) within 6 months of enrollment (catheterization efficiency)

IV.D. Rationale for the Selection of Outcome Measures

Rationale for Clinical Assessments

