Myocardial infarction will be characterized according to the 4th Universal MI definition for both spontaneous and for periprocedural MI⁵¹ MIs.

Hospitalizations

All, cardiovascular, non-cardiovascular, and for progressive or unstable angina. Urgent and unscheduled hospitalizations for other cardiovascular causes that do not meet the criteria for the specific events listed above will be classified as hospitalization for other cardiovascular causes (e.g., hospitalization for cardiac chest pain that does not meet the criteria for MI, hospitalization for arrhythmias, hospitalization for pulmonary embolism). Non-cardiovascular hospitalization are defined as any hospitalization whose primary cause is not thought to be CV in nature.

Preventive medication use

Information on preventive medication use will be acquired at study entry and 45 days. Participants with a clear clinical indication for use of ASA/antiplatelet agents and or, statins eg: hyperlipidemia, diabetes, documented CAD, will be characterized according to use/nonuse for each medication class.

Radiation safety endpoint – cumulative dose at 1 year

The cumulative radiation exposure over the 12 months following enrollment will be calculated based on the participant's exposure to radiation for cardiovascular care from one or more of the following modalities. For cCTA, the administered radiation dose (computed tomography dose index volume and dose length product for cCTA) will be recorded by the individual sites. For stress nuclear imaging, the radiotracer dose(s) will be collected and converted to equivalent radiation doses for comparison to cCTA. For ICA, the radiation dose from fluoroscopy administered will be recorded by sites and converted using standardized approaches to allow for comparison to radiation from cCTA. In instances in which the information required to assess actual dose is not available, a standard

dose based on accepted average exposures will be imputed for that form of testing. Cumulative radiation exposure from additional cardiac testing and procedures during the entire follow-up period will also be collected.

Catheterization efficiency

The proportion of invasive cardiac catheterization patients who undergo revascularization (PCI or CABG) within 6 months of enrollment will be determined.

VII.C Testing Complications and Reporting

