4.1.2 Additional Protocol Specified Endpoints

Additional protocol-defined endpoints include:

1. Death, including separate analyses for all-cause and cardiovascular
2. Nonfatal MI, including separate analyses for all, procedural, and spontaneous
3. Hospitalizations, including separate analyses for all-cause, cardiovascular and for progressive or unstable angina.
4. Preventive medication use, defined as use of aspirin/anti-platelet drugs and/or statins, in participants with clinical indication for use
5. Cumulative trial strategy-related radiation exposure
6. Proportion of participants who undergo revascularization (PCI or CABG) within 6 months of diagnostic catheterization, overall, and controlling for rates of diagnostic catheterization.

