9.3.3.6 Prevention Motivation

Prevention motivation information will be assessed at study entry and during the participant follow-up at 45 days, 6 months and 12 months. Specifically, this includes an assessment of the importance of cardiac risk prevention to the participant's future health (5 point Likert scale from not important>>>very important) at baseline, 45 days and 12 months, as well as an assessment of whether the PRECISE evaluation changed the participant's motivation to modify cardiac risk factors and improve heart health, and an inquiry regarding how their testing results were communicated by their healthcare provider (asked at 45 days and 12 months). The number (%) will be summarized between the precision care arm and usual care arm and compared using Pearson's chi-square test at entry, 45 days and 12 months.

1. Participants will be characterized by reported cardiac risk prevention importance at baseline and post evaluation at 45 days and 12 months by randomized arm, testing received, and testing results
2. Among participants receiving testing by 45 days, will be characterized by response at 45 days by randomized arm, testing received, and testing results as having:
 1. Increased my motivation
 2. Did not change my motivation
 3. Decreased my motivation
 4. I don't know the results of my evaluation
3. Among those tested by 45 days and who received test results, method of communication of testing results will be characterized by response at 45 days by randomized arm, testing received, and testing results
4. Among those who received test results, association of the method of communication (method of sharing test results) reported at 45 days and reported change in motivation overall and by test results

5. The association of medication use (antiplatelet usage, lipid lowering medication usage, and anti-hypertensive medication usage) and change in motivation responses (increase, decrease no change, did not receive) and rates of medication use (aspirin/anti-platelet agents and statins) at 45 days and 12 months

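### SAP 9.3.3.3 compares preventive-medication use by chi-square with no baseline-adjusted effect estimate, and does not test the indicated-population statin endpoint that SAP 4.1.2 and the protocol list

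*SAP*

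**What the plan says.** SAP 4.1.2 lists the endpoint as "Preventive medication use, defined as use of aspirin/anti-platelet drugs and/or statins, in participants with clinical indication for use". The final protocol agrees. Section IV.C has "Rates of preventive medication use (ASA, statins) in participants with clinical indication for use", and section VII.B says that participants with a clear indication "will be characterized according to use/nonuse for each medication class".

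SAP 9.3.3.3 sets out the analysis. On data it says: "New and total use of preventative medication will be collected during baseline and the participant follow-up at 45 days, 6 months and 12 months". It defines three classes: antiplatelet, lipid-lowering and antihypertensive. For lipids: "Lipid Lowering Medication usage is defined as the usage of any of the following medications: Statins or Other Lipid Lowering Agents". The arms are compared by Pearson's "chi-square test for the following combinations", namely "usage at baseline and 45 days, 2) usage at baseline and 6 months, and 3) usage at baseline and 12 months". The section gives no model, stratification, effect measure or confidence interval, and no restriction to participants with an indication.

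The only other SAP text on statin rates is in 9.3.3.6, "rates of medication use (aspirin/anti-platelet agents and statins) at 45 days and 12 months". That item concerns the association with change in motivation and is not an arm comparison. SAP section 3 says the SAP takes precedence over the protocol on endpoints and analyses. SAP section 11 declares one change only, the added day in the time-to-event calculation.

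**The concern.** There are two problems.

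**Method.** Use of a drug before randomisation should predict use of the same drug afterwards strongly. The trial collects it, yet the plan does not say how it enters the comparison. One analyst could test follow-up use alone; another could test the four-cell table of baseline by follow-up use. These are different tests with different power, and neither is specified to yield a baseline-adjusted arm difference with an interval. The SAP does use the baseline score as a covariate for quality of life (9.3.2).

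**Endpoint.** The class analysed for lipids is wider than the class listed, and the population is wider than the population listed. As written, no arm comparison addresses statin use in participants with an indication.

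This matters because the protocol's background (III.A) reports greater aspirin and statin use after cCTA and offers medication use as one possible driver of fewer infarctions. A result for any lipid-lowering agent in all participants speaks to that argument only indirectly.

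**Working it through.** **Endpoint, by comparing the texts**

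| | SAP 4.1.2; Protocol IV.C and VII.B | SAP 9.3.3.3 |
|---|---|---|
| Lipid class | Statins | Statins or any other lipid-lowering agent |
| Population | Participants with a clinical indication | No restriction stated |
| Declared in SAP 11 | – | No |

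No assumption is needed for this part.

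**Method, by arithmetic**

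The documents state no rate, effect, sample size or power for this endpoint, so there is no figure of the plan's own to reproduce. The rates below are assumptions. The number per arm, 945, is borrowed from the protocol's quality-of-life section (90% of 1050).

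Let b be baseline use, c continuation among baseline users, and s new starts among baseline non-users. Follow-up use is p = bc + (1−b)s. The variance after conditioning on baseline use, as a fraction of the unadjusted variance, is

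ratio = [b·c(1−c) + (1−b)·s(1−s)] / [p(1−p)].

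Over b = 30-60%, c = 85-95% and s = 5-25%:

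- Smallest, at b = 0.50, c = 0.95, s = 0.05: p = 0.50, ratio = (0.02375 + 0.02375)/0.25 = 0.19.
- Largest, at b = 0.30, c = 0.85, s = 0.25: p = 0.43, ratio = (0.03825 + 0.13125)/0.2451 = 0.69.

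Worked example: b = 0.45, c = 0.92, new starts 15% against 20%, 945 per arm, two-sided 5%.

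- Follow-up use is 0.4965 against 0.5240, a difference of 0.0275.
- Follow-up alone: SE = √[(0.2500 + 0.2494)/945] = 0.0230, z = 1.20, power 22%.
- Adjusted for baseline: SE = √[(0.1032 + 0.1211)/945] = 0.0154, z = 1.78, power 43%.
- Joint four-cell table, 3 df: only the two baseline-non-user cells differ between arms, each by 0.0275, with pooled probabilities 0.09625 and 0.45375. The noncentrality is 2 × 945 × 0.01375² × (1/0.09625 + 1/0.45375) = 4.5, power 40%.

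Simulations at 945 per arm (4000 runs each):

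| Baseline use | Continuation | New starts | Follow-up alone | Joint table | Cochran-Mantel-Haenszel |
|---|---|---|---|---|---|
| 40% | 90% | 15% vs 22% | 0.45 | 0.71 | 0.72 |
| 40% | 80% | 20% vs 27% | 0.46 | 0.65 | 0.61 |
| 40% | 90% | 15% vs 15% (null) | 0.046 | 0.049 | 0.048 |

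All three tests hold their level. Testing follow-up use alone loses clearly. The joint table is close to the stratified test on power and sometimes ahead of it.

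**The case against.** The strongest objection is that the text does not describe a bare follow-up comparison. It pairs baseline with each visit as combinations and speaks of new as well as total use, so baseline use may already be in the table. On that reading the power loss nearly vanishes. This stands: a reader might infer that the plan certainly throws away precision, and the documents do not establish that. What remains is that the sentence supports two tests, and the joint test answers a four-cell question. It reacts to chance differences at baseline as well as to the effect, and it returns neither a direction nor an estimate.

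A reader might also infer bias. There is none. Under 1:1 randomisation the unadjusted test is valid, as the null simulation shows.

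The endpoint is an additional one, outside the list of secondary endpoints under Benjamini-Hochberg control, with no power claim. That also stands and limits the importance of the point. So does the fact that every rate above is assumed, and that the indicated population would be smaller than 945 per arm by an amount the documents do not give.

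Finally, it would be too strong to say that statins have been dropped from the trial. SAP 4.1.2 still lists them, and the table shells are in a separate document. The gap is that 9.3.3.3 writes no arm comparison for statins alone or for the indicated population.

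**Conclusion.** The point holds as one of efficiency and endpoint alignment.

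The alignment part rests on the text alone: 9.3.3.3 does not test the endpoint in SAP 4.1.2 and the protocol, in drug class or in population, and section 11 does not say so.

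The efficiency part depends on the reading. If follow-up use is tested alone, baseline adjustment would reduce the variance to about 19-69% of its unadjusted value, and power in the worked example would rise from 22% to 43%. If the joint table is tested, the difference is small (40% against 43%) and the defect is the missing direction and effect estimate. These sizes rest on assumed rates and a borrowed sample size; they show scale and do not predict this trial's power. A revision is worthwhile because it is cheap and settles both parts.

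**What to change.** In SAP 9.3.3.3:

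1. Replace the combinations sentence with one 1-df arm comparison per class and visit, adjusted for or stratified by baseline use of that class: Cochran-Mantel-Haenszel, or logistic regression with a standardised risk difference and 95% CI.
2. Report new starts among baseline non-users by arm, with an interval.
3. Add statin use and aspirin/antiplatelet use, each in participants with a clinical indication, as comparisons of their own to match 4.1.2. Define the indication from baseline data. Documented CAD is one of the protocol's listed indications and can be a finding of the assigned test, so a definition using later results could select different participants in the two arms.
4. Keep any lipid-lowering agent and the all-participant analysis as supportive.
5. List any remaining departure from the protocol in section 11.

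The cost is SAP wording, the matching table shell and a standard procedure. No new data should be needed: baseline and follow-up use are collected, statins are named separately from other lipid-lowering agents, and diabetes and dyslipidemia are already inputs to the PROMISE score (SAP 6.1).
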